TRADITIONAL MONGOLIAN SWADDLING AND DEVELOPMENTAL DYSPLASIA OF THE HIP: A RANDOMIZED CONTROLLED TRIAL

RESEARCH PROTOCOL

[name] and SMOPP team
National Center for Maternal and Child Health, Mongolia
29 June, 2019

SUMMARY

Background

In Mongolia, swaddling is an ancient practice and nowadays it still remains common child care in the first months of life. Mongolian traditional way of swaddling technique involves tight, prolonged wrapping from the head or neck down in two to three layers of thin cotton cloth, covered by layers of thick blankets and binding with 2-3 tiers for whole day. This traditional prolonged swaddling where arms and legs are extended and hips are in adduction position might increase the risk for developmental dysplasia of the hip (DDH). DDH is a major health problem that can lead to lifelong disability if diagnosis is missed in first weeks of life. Mongolia is the first Asian country that launched a universal ultrasound hip screening (Graf's method) for DDH in newborns. All DDH cases are followed up on monthly basis by hip ultrasound and treated with a simple extension and abduction orthosis if necessary.

Objectives

To test the effect of traditional swaddling on the DDH in Mongolia

Design

A prospective, randomized trial with two study groups will be conducted in Mongolia. The term newborns with Graf Type 2a (physiologically immature) will be randomly allocated to one of two groups. The intervention/"non-swaddling" group will be instructed not to swaddle at all. The control/"swaddling group" will be swaddled in the common traditional Mongolian method. Both groups will be followed up by Graf's method of hip ultrasound at 4-6 weeks' intervals until healing according to Mongolian national guideline. All infants in need of therapy (Graf type 2a-, 2c or worse) will be treated with Tubinger orthosis. At around 12 months of age all children will be checked again by Graf's method of hip ultrasound.

Timeline and Analysis

The study will be conducted between August 2019-March 2021. Findings will be reported in March-June 2021. Analysis will be intention to treat.

Ethics

The study protocol will be reviewed and approved by the Institutional Review Board at the National Center for Maternal and Child Health and the Ethical Review Committee of Ministry of Health, Mongolia prior to start the study.

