2. OBJECTIVES

Mongolian traditional prolonged swaddling where arms and legs are extended and hips are in adduction position increases the risk for DDH. This hypothesis is going to be tested in this study.

The primary outcomes: The number of “non-Type 1” hip cases at the monthly follow-up ultrasound control visits

The secondary outcomes:

- a. number of DDH cases (Graf Type 2a-, Type C, D and Type 4) at any monthly follow-up ultrasound control visits and rim defects at 12 months’ follow-up
- b. correlation between the primary outcome and the swaddling frequency (in hours per day) and swaddling duration (in days)
- c. primary and secondary outcomes association with the swaddling.

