3.2. Sampling and randomization

Study site: The National Center for Maternal and Child Health (NCMCH) is purposely selected as a study site. Approximately 50% of all deliveries in Ulaanbaatar occur in the center and there are about 11,000 live births annually. As the center is a specialized tertiary care level teaching hospital, it is responsible for providing services for follow-up ultrasound controls and treatment of DDH cases in Ulaanbaatar. There are two term-delivery units with 6 neonatologists/screeners, a preterm-

delivery unit with 6 neonatologists/screeners and a pediatric radiology unit with 6 radiologists. Data will be collected from September 2019 to March 2021.

Sample size calculations: The primary outcome of interest is dichotomous (Graf Type 1 or non-Type 1 hips). If we assume that 10% of the subjects on the non-swaddled group has a non-Type 1 hip and it is of clinical relevance only if we observe a 30% (effect size) absolute non-improvement for those on the swaddled group (i.e. 40% of the subjects will have a non-type 1 or worst hip).

For a two-sided test of 5%, a formula to calculate the sample size is given by

$$N (\text{size per group}) = c * \frac{\pi_1(1 - \pi_1) + \pi_2(1 - \pi_2)}{(\pi_1 - \pi_2)^2}$$

where $c = 7.9$ for 80% power, and $\pi_1=0.2$ and $\pi_2=0.4$

For a 80% power, we have $N (\text{size per group}) = 7.9 * [0.1 (1 - 0.1) + 0.4 (1 - 0.4)]/(0.1-0.4)^2 = 29$

Hence minimum $29 * 2 = 58$ subjects are needed.

In order to increase the statistical power, and assuming at least a 20% dropout, it is decided to include about 40 subjects in each group.

Sampling: There are 6 neonatologists/screeners at post-delivery wards of the hospital who perform the hip ultrasound screening. Out of the 6 neonatologists/screeners, one neonatologist will be assigned as a data collector for the study to reduce a baseline diagnostic bias. On the first days after birth, all newborns of the data collector will be screened using Graf's method of ultrasound according to the Mongolian National Guideline.⁸ After the screening, we will generate a list of all newborns with Graf Type 2a hips on daily basis. All term newborns with Graf Type 2a cases (physiologically immature) will be eligible for the study.

Subject inclusion criteria

Predefined inclusion criteria will be:

1. Term newborns with confirmed Type 2a hips
2. Parents who are able to return for the scheduled follow-up ultrasound examination during the study period

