3.4. Outcome assessments

The primary outcome of the study will be the number of “non-Type 1” hip cases at the any monthly follow-up ultrasound control visits.

The secondary outcomes are:

- a. number of DDH cases (Graf Type 2a-, Type C, D and Type 4) at any monthly follow-up ultrasound control visits
- b. correlation between the primary outcome and the swaddling frequency (in hours) per day and swaddling duration in days
- c. primary and secondary outcomes association with the swaddling.

Operational definitions

Swaddled: Newborns are swaddled in the common traditional Mongolian method at least 20 hours per day for 4-6 weeks

Non swaddled: Newborns are not swaddled at all.

The “non-Type 1” hip case: a neonate who’s Graf ultrasound type is other than Type 1 at any monthly follow-up visits

Physiologically immature or Graf Type 2a hip: has a certain degree of physiological delay in ossification of the bony acetabular roof. The alpha angle is between 50 and 59, the beta angle is between 55 and 77, and the patient is younger than 6 weeks of age.

Graf Types 2a- and 2a+: Starting from 55° alpha at 6 weeks of age and assuming a spontaneous maturation of 1° per week. Type 2a+ is still considered to be physiological while 2a- hips are assigned to the group of DDH.

Swaddling hours: according to the 24-hour diaries of swaddling and non-swaddling patterns of mothers and research assistants' compliance check reports

Swaddling days: according to the 24-hour diaries of swaddling and non-swaddling patterns of mothers and research assistants' compliance check reports

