6. EXPECTED OUTCOMES AND DISSEMINATION OF THE FINDINGS

We hypothesize that the swaddling would be harmful to Graf Type 2a hips. The results will be published in national and international journals. Also a booklet with a summary of the research findings, including the recommendations, will be produced and distributed to. To make our research findings known to the participating communities, the research team will disseminate the project results through Radio/TV programmes.

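### The hypothesis is about DDH, but the primary outcome also counts Type 2a and 2a+ hips that the protocol calls physiological, so a positive primary result cannot by itself show an effect on DDH

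*Protocol*

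**What the plan says.** The Objectives paragraph of the protocol Summary reads "To test the effect of traditional swaddling on the DDH in Mongolia". Section 2 states the hypothesis to be tested: "Mongolian traditional prolonged swaddling where arms and legs are extended and hips are in adduction position increases the risk for DDH".

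The primary outcome, in Sections 2 and 3.4, is the number of non-Type 1 cases. Section 3.4 defines such a case as an infant whose "Graf ultrasound type is other than Type 1 at any monthly follow-up visits". Neither section excludes Type 2a or 2a+. Section 3.2 sizes the trial on this same split between Type 1 and everything else.

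Section 3.4 also says which types are DDH. A Type 2a hip (under 6 weeks of age) "has a certain degree of physiological delay in ossification of the bony acetabular roof". For the later subdivision, "Type 2a+ is still considered to be physiological while 2a- hips are assigned to the group of DDH".

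DDH is counted separately as secondary outcome (a): "number of DDH cases (Graf Type 2a-, Type C, D and Type 4) at any monthly follow-up ultrasound control visits".

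Section 6 words the hypothesis differently: "We hypothesize that the swaddling would be harmful to Graf Type 2a hips".

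**The concern.** The objective and hypothesis name one condition, and the primary outcome counts a wider one. Only infants with confirmed Type 2a hips are enrolled, and the first control is at 4-6 weeks. An infant who is still Type 2a at that visit, or is graded 2a+ at six weeks or later, is a primary-outcome case. Under the protocol's own definitions that infant does not have DDH.

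What is at stake is the conclusion that the primary result can carry. If swaddling only slows maturation, the primary test can be clearly positive while DDH is equally frequent in both arms. Read against the hypothesis in Section 2, that result would look like confirmation that swaddling raises the risk of DDH. The protocol does not say that the primary result must be read more narrowly.

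**Working it through.** **1. Which types count where (Section 3.4)**

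| Graf type at a follow-up visit | Primary-outcome case | DDH under the protocol |
|---|---|---|
| Type 1 | no | no |
| 2a (under 6 weeks) | yes | no |
| 2a+ | yes | no |
| 2a- or worse | yes | yes |

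DDH is a subset of the primary outcome. In each arm, primary rate = DDH rate + rate of infants who are only 2a/2a+.

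**2. The protocol's sample size (Section 3.2)**

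Inputs: 10% non-Type 1 without swaddling, 40% with swaddling, two-sided 5%, 80% power, c = 7.9.

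N = 7.9 × [0.1 × 0.9 + 0.4 × 0.6] / 0.3² = 7.9 × 0.33 / 0.09 = 28.97, so 29 per group. The stated figure reproduces. With 20% dropout, 29 / 0.8 = 36.25, so 37, which about 40 per group covers. Forty per group leaves 40 × 0.8 = 32 after that dropout.

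No DDH rate enters this calculation.

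**3. A positive primary result with no effect on DDH**

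Assumed rates, since the protocol gives none:

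- Non-swaddled: DDH 2% + only 2a/2a+ 8% = 10%
- Swaddled: DDH 2% + only 2a/2a+ 38% = 40%

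These totals are the planning rates. Power, normal approximation with pooled variance under the null:

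Φ{ [0.3√n − 1.96√(2 × 0.25 × 0.75)] / √0.33 }

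- n = 32: (1.697 − 1.200) / 0.574 = 0.865, power 81%
- n = 40: (1.897 − 1.200) / 0.574 = 1.213, power 89%

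The primary test depends only on the totals, so this power is the same whatever share of the cases is DDH.

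**4. What secondary outcome (a) could show**

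The screening figures in Section 1 (1.2% dysplastic, 1.3% incidence of DDH) are not rates for infants who start as Type 2a. All rates below are therefore assumptions. The method is the same as in step 3.

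| DDH, non-swaddled vs swaddled | n per group for 80% power | Power at 40 | Power at 32 |
|---|---|---|---|
| 1% vs 5% | 285 | 18% | 15% |
| 2% vs 10% | 138 | 32% | 27% |
| 5% vs 15% | 141 | 32% | 26% |
| 5% vs 20% (half of all non-Type 1 cases) | 76 | 53% | 44% |
| 2% vs 20% | 47 | 74% | 64% |
| 7.5% vs 30% (three quarters of cases) | 47 | 74% | 64% |
| 5% vs 30% | 36 | 85% | 76% |
| 10% vs 40% (all cases are DDH) | 32 | 89% | 81% |

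The approximation flatters the small rates. Fisher's exact test at 5% vs 20% has 28% power at 32 per group and 41% at 40. Among these rows, 80% power at 40 per group is reached only at 5% vs 30%, or when every non-Type 1 case is DDH.

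**The case against.** The strongest case for the plan has three parts.

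- **A maturation endpoint has a stated rationale.** Section 1 notes that it is disputed whether hips below 60° alpha are pathological or merely immature, and says that such hips could go on to lasting dysplasia if the infant is swaddled. The Section 6 hypothesis, harm to Type 2a hips, already fits the primary outcome. This stands as a reason for choosing the outcome. It does not turn 2a or 2a+ into DDH under Section 3.4.
- **The hypothesis is not tested by the primary outcome alone.** DDH is the first secondary outcome. Annex 4 Tables 2 and 3 give None-Type 1 and DDH separate rows by arm. If each infant is counted by the worst type seen, subtracting one row from the other gives the purely physiological cases. This also stands, and it makes an extra table row optional.
- **An intermediate primary outcome may be the feasible one.** The table above supports this: most of the DDH scenarios need more than 40 per group. It justifies the endpoint, but not a hypothesis worded as DDH.

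A reader might also infer more than the protocol supports:

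- That the primary outcome says nothing about DDH. It includes every DDH hip, so the limit is only that it cannot show a DDH effect by itself.
- That a large share of normally maturing infants must become cases. Adding 1° per week from birth, whole-degree starting values of 50-55° (6 of 10) are below 60° at 4 weeks, and 50-53° (4 of 10) at 6 weeks. But Section 3.4 gives that rate only from 6 weeks of age, the count is of degree values and not infants, and Section 3.2 plans for 10% in the non-swaddled arm. Nothing here relies on it.
- That Section 6 commits the trial to announcing a DDH effect from the primary result. It says only that results will be disseminated.

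**Conclusion.** The mismatch is real and lies in the current text: the objective and the Section 2 hypothesis concern DDH, while the primary outcome mixes DDH with types that the protocol classes as physiological. That follows from the definitions alone and needs no numerical assumption.

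The size of the problem depends on what share of non-Type 1 cases is DDH, which the protocol does not give. At one extreme, all of the planned 30-point difference could be 2a/2a+ with no DDH effect, as in the 2%/2% illustration. At the other, if all cases were DDH, the two outcomes would coincide and the concern would vanish. In between, the DDH comparison has limited power at the planned size, from 15% to 74% in the first six assumed scenarios at 32 to 40 per group. A positive primary result could thus stand beside an inconclusive DDH result.

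The trial is not without evidence on DDH, and the choice of primary outcome is defensible. What is not supported is a DDH conclusion drawn from the primary result.

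**What to change.** In the Summary and Section 2, state the primary hypothesis as delayed maturation of Type 2a hips to Type 1, in line with Section 6. Add a sentence that any claim about DDH will rest only on secondary outcome (a), and that the trial is not sized for that outcome.

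Optionally, add a row to Annex 4 Tables 2 and 3, beside the existing DDH row, for non-Type 1 infants who were only ever 2a or 2a+, by arm.

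The cost is a few sentences and at most one row per table, from data already collected. Sample size, visits and tests do not change. The downside is a more modest headline claim. If the sponsor wants DDH to be the headline, the alternative is to make it primary and recompute the sample size from a justified DDH rate in infants who start as Type 2a, which could require far more than 40 per group.

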3.5. Statistical analysis

Data will be double computerized using EpiData (The EpiData Association Odense, Denmark) and analyzed using Stata software 9 (Stata Corporation). All ultrasound examination pictures will be uploaded to the HipScreen platform.

Balance checks for the “swaddling” and “non-swaddling” groups will be conducted and reported for all key individual-level variables measured at baseline, including age at hip ultrasound screening in days, gender, risk factors (birth weight ≥ 4000 gr, breech delivery, family DDH history, parity etc.), Graf hip type, alpha angles at baseline and management.

The primary and secondary outcomes will be described as percentage adjusted for the available baseline variables. Outcomes will be evaluated in an intent-to-treat analysis. Univariate analyses will assess factors that will be associated with outcomes and identify potential confounders (with rate ratios of ≥ 2) or variables that differed between study groups at enrollment. These covariates will be included in multivariate analyses. Multivariate logistic regression will be used to estimate the adjusted risks for prevalent outcomes. Pearson's correlation coefficient will be calculated between “non-Type 1” and swaddling days and swaddling hours per day.

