3. STUDY METHODOLOGY

3.1. Study design

A prospective interventional randomized controlled trial with two study groups will be conducted in Mongolia.

“Swaddling” group: The newborns randomized into the “swaddling” group will be swaddled in the common traditional Mongolian method at least 20-24 hours every day for 4-6 weeks. Traditional swaddling in Mongolia is as follows: Swaddling is a tightly wrapping (2 adult fingers pass under the cloth) of a baby in several layers of cloth, covered by one warmer blanket from head and neck to toe in a straight position after birth for day and night time. Two or three ropes are used across a baby's body for binding to avoid unwrapping. Since the non-swaddling clothes have to be provided with alternatives to the readily available swaddling clothes and blankets, the swaddled group will be given a blanket and several cotton sheets at the time of recruitment.

“Non-swaddling” group: The “non-swaddling” group will be instructed not to swaddle at all for 4-6 weeks. The required size and warmth of clothing required to keep a newborn infant warmly clothed will be provided to the family. Also, wide warm sleeping bags that allow free legs movements will be provided to prevent swaddling when go outdoors.

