3. Analysis of the 7-days prospective mother's diaries used for sleeping and crying/fussing outcome measure: as mother's own reported behaviour during 2 time periods
4. Unscheduled visits from a monitoring research assistants: in order to estimate unreported non-compliance conducted for all families 1 to 3 times
5. End-study research assistant impressions' questionnaire: of their impression about compliance in each family and the consistency and extent of accuracy of the reports from each family during each week of child's life

For analysis, the first and third methods of exposure recordings above will be quantifiable and will be combined to reveal exposure to swaddling per child for use in per-protocol analysis. The other three methods detailed above will be triangulated with the data from the diaries.

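### Secondary outcome b rests on a Pearson correlation with no arm term, which would mainly restate the randomised contrast and should not be read as evidence that more swaddling is worse

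*Protocol*

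**What the plan says.** Section 3.4 (and section 2 in nearly the same words) makes secondary outcome b the "correlation between the primary outcome and the swaddling frequency (in hours) per day and swaddling duration in days". Section 3.2 calls the primary outcome dichotomous: Graf Type 1 or not. Section 3.5 fixes the method: a Pearson "correlation coefficient will be calculated between" non-Type 1 status and the two exposure measures. It mentions no arm term, no stratification and no restriction to one arm.

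Section 3.1 sets the exposure by arm. The swaddling group is to be swaddled "at least 20-24 hours every day for 4-6 weeks"; the other group is "instructed not to swaddle at all for 4-6 weeks". Section 3.3 expects some families in the non-swaddling group not to adhere, but gives no rate.

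Exposure is described in two places:
- Section 3.3 lists five sources. It says that "the first and third methods of exposure recordings above will be quantifiable and will be combined to reveal exposure" to swaddling per child, for the per-protocol analysis. The first source is a 24-hour recall taken at weekly home visits. The third is a 7-day mother's diary kept in two periods, described as "diaries used for sleeping and crying/fussing outcome measure".
- Section 3.4 gives "Swaddling days: according to the 24-hour diaries of swaddling and non-swaddling patterns of mothers", together with the research assistants' compliance reports, and defines swaddling hours in the same way.

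**The concern.** The trial's hypothesis is that swaddling harms immature hips. A positive correlation with hours and days will naturally be read as a gradient, that is, as evidence that more swaddling does more harm. The design puts the infants into two clusters of exposure, one near zero and one at 20-24 hours. A coefficient over both clusters responds to the gap between them, which the primary comparison already estimates, and hardly at all to differences in exposure among swaddled infants. Outcome b could then appear to confirm the primary result independently when it adds almost nothing to it.

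Even where it is informative, a Pearson coefficient with a 0/1 variable gives no change in risk per hour or per day.

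A lesser matter is the exposure variable. Sections 3.3 and 3.4 do not name the same sources, and the 7-day diary is labelled for an outcome that appears in neither section 2 nor section 3.4. The sources as described do not observe every day.

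**Working it through.** **Inputs.** From section 3.2: non-Type 1 rates of 10% and 40%, two-sided 5%, about 40 per group, at least 20% dropout (40 × 0.8 = 32 evaluable). From section 3.1: 20-24 hours a day for 4-6 weeks against none. Non-adherence is my assumption, 0-50%, since the protocol gives no figure.

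**The plan's own figure.** 7.9 × (0.1 × 0.9 + 0.4 × 0.6) / 0.3² = 28.97, so 29 per group is reproduced. One line of section 3.2 prints π1 = 0.2, but the text and the worked calculation use 0.1, as I do.

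**Arm against outcome.** With 1:1 allocation the overall rate is 0.25, and

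phi = (0.40 − 0.10) × 0.5 / √(0.25 × 0.75) = 0.346.

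**Hours against arm.** Take hours as uniform on 20-24 in one arm and 0 in the other. The between-arm variance is 22²/4 = 121. The average within-arm variance is (4²/12)/2 = 0.667. The correlation of hours with arm is √(121/121.667) = 0.997.

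**Hours against outcome, no effect of exposure within arm.** If outcome and hours are related only through arm, r = phi × corr(hours, arm) = 0.346 × 0.997 = 0.345, which is phi for practical purposes.

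**Simulation** (4,000 trials per setting). Outcome risk depends on assigned arm only. Hours are uniform on 20-24 and days on 28-42 in the swaddling arm, 0 in the other. Assumed non-adherers, in both arms, receive 0-20 hours and 1-42 days.

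| Non-adherence | corr(hours, arm) | mean r, hours | significant, 32 per arm | significant, 40 per arm |
|---|---|---|---|---|
| 0% | 0.997 | 0.35 | 83% | 90% |
| 10% | 0.93 | 0.32 | 76% | 85% |
| 20% | 0.86 | 0.30 | 69% | 79% |
| 30% | 0.79 | 0.27-0.28 | 61% | 69% |
| 50% | 0.63 | 0.21-0.22 | 42% | 49% |

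For days under full adherence the mean r is 0.34, significant in 82% and 89% of trials. Within the swaddling arm alone the mean r for hours is about 0 and is significant in 3-5% of trials, as it should be when exposure has no effect there.

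**What a within-arm analysis could detect.** With 80% power, r = tanh(2.80/√(n − 3)): 0.48 at n = 32 and 0.43 at n = 40.

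**Days observed.** Weekly recalls alone cover 4 of 28 or 6 of 42 days (14%). Two 7-day diaries add at most 14 days if none overlap: 18/28 = 64% or 20/42 = 48%. If about half of the days are swaddled and the observed days are a random sample of D days, of which k are observed, the 95% error of the extrapolated count is 1.96 × D × √[0.25/k × (D − k)/(D − 1)]. That is about ±13 to ±16 days from recalls alone and ±4 to ±7 days with the diaries.

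**The case against.** The strongest reply is that the coefficient need not be a pure copy of the arm effect. Section 3.3 expects cross-over in the non-swaddling group, and then actual exposure differs within arms. The simulation also ties risk to assigned arm even for infants who crossed over, which is a worst case. This stands, so a reader who infers that the correlation only repeats the arm contrast goes too far: that is close to exact only under near-full adherence. Cross-over does not rescue the analysis, however. The added variation comes from families' choices rather than randomisation, and one coefficient cannot separate it from the arm effect.

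The protocol does not say that the coefficient is computed over both arms, and it speaks of correlation rather than dose-response. Use of all infants is inferred from the absence of any arm term or restriction; it is the plain reading of section 3.5.

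A reader might also infer that swaddling days cannot be obtained because weekly recalls see only 14% of days. The document does not support that. Section 3.3 adds the 7-day diaries, and section 3.4 adds compliance reports. Duration could also mean the time until a family stopped swaddling, which weekly visits would bracket to about a week. The sleep and crying label does not prevent the diary from recording swaddling, and the rule for deriving days may properly sit in an analysis plan that is not at hand.

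Finally, this is one secondary outcome. The intention-to-treat comparison and the adjusted logistic regression are not affected.

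**Conclusion.** The concern holds for the stated method. As section 3.5 is written, the coefficient would mainly restate the randomised contrast. Under full adherence and no within-arm effect it sits at about 0.35, against 0.346 for arm alone, and is significant in about 83-90% of trials at 32-40 per arm. With an assumed 10-50% non-adherence it falls to about 0.32-0.21 and is significant in about 85-49% of trials at 40 per arm (76-42% at 32). In neither case does a positive value show that more swaddling is worse than less.

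These figures rest on the planning rates of 10% and 40%, on the assumed spread of hours and days, and on risk that follows assigned arm.

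On exposure, the supportable claim is limited: the recalls and the two diaries together observe at most about half to two thirds of the days, so swaddling days would be an estimate and not a count, and sections 3.3 and 3.4 should name the same sources.

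**What to change.** In section 3.5, replace Pearson's coefficient with logistic regression of non-Type 1 status on mean swaddling hours per day and, in a separate model, on swaddling days. Include arm and baseline alpha in each model, or fit within each arm in which exposure varies. Report an odds ratio per hour or per day with its confidence interval, labelled exploratory and observational.

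In sections 3.3 and 3.4, state one set of exposure sources, and describe the 7-day diary as an exposure diary if that is its use here. At each weekly visit, ask on how many of the past 7 days the infant was swaddled, so that days can be counted.

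The cost is a change of wording and one question at visits already planned. The drawback is precision. With good adherence, arm explains 121/121.667 = 99.5% of the variance in hours, so arm and hours are nearly collinear. At 32 per arm, about 0.4 × 32 + 0.1 × 32 = 16 events must support three coefficients. Only a within-arm correlation of about 0.43-0.48 would be detected with 80% power. The report should say so, and should not take a null result as absence of a gradient.

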For babies assigned to the “swaddling” group, parents will be instructed to follow a pattern of traditional Mongolian swaddling as described above. For babies assigned to the “non-swaddling” group, parents will be instructed to do not swaddle at all and only use a wide sleeping bag with free leg position.

Trained research assistants will make home visits on weekly basis until the infants are 4-6 weeks of age to check and monitor the compliance of the families by observing the baby during every home visit and collecting retrospectively 24-hour diaries of swaddling and non-swaddling patterns. Also unscheduled visits from monitoring research assistants will be organized to estimate unreported non-compliance conducted for all families 2 to 3 times.

At 4-6 weeks follow up visit, the babies will be checked by Graf’s method of hip ultrasound performed by a trained radiologist uninformed about the initial status of the hips. Regardless of the study group, monthly controls will be fixed until complete maturation to Graf type 1 is documented. Families, who did not show up for follow-up will be contacted by phone or home

visit. In cases when the parents will not be able/willing to come to the follow-up control visit(s), the PI will visit the family and make the follow-up ultrasound examination at their home using a portable ultrasound device (MicroUs EXT-1H, REV:C). All infants in need of therapy (Graf type 2a-, 2c or worse) will be treated with Tubinger orthosis.

Monitoring: In the non-swaddling group, it is expected that some families would not adhere to their instructions of not swaddling because of grandparents/cultural pressures. To monitor compliance and obtain a measure of exposure, multiple sources of information will be used:

1. A retrospective 24-hour history of swaddling/clothing: will be recorded by research assistants during each weekly home visit through recording the carer's descriptions of the style of dress/clothing/ swaddling and length of each during the past 24-hour within the 24-hour retrospective diaries (a kind of behaviour diary adapted to record swaddling/clothing pattern)
2. Direct observation of research assistants during weekly visits: of the dressing/clothing/ swaddling of each child and discreetly recording observations of the type of baby clothing items that each family washed and hung to dry on the day of visit (available for observation during the majority of visits)

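### The planned correlation of non-Type 1 hips with swaddling days cannot answer the duration question: pooled it mostly repeats the arm contrast, and within the swaddled arm it is confounded with age at the scan

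*Protocol*

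**What the plan says.** Secondary outcome b (Protocol sections 2 and 3.4) relates the primary outcome to swaddling hours per day and swaddling duration in days. Section 3.5 gives the method: a Pearson's "correlation coefficient will be calculated between" non-Type 1 status "and swaddling days and swaddling hours per day". It names no analysis population and no adjustment for this coefficient.

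Four other statements bear on it.

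- Section 3.1: the swaddling group is swaddled "at least 20-24 hours every day for 4-6 weeks". The other group is told not to swaddle at all over the same period.
- Section 3.3, first follow-up: "At 4-6 weeks follow up visit, the babies will be checked by" hip ultrasound. Research assistants "make home visits on weekly basis until the infants are 4-6 weeks of age", so weekly exposure recording ends in the same window.
- Section 3.4, exposure: "Swaddling days: according to the 24-hour diaries of swaddling and non-swaddling patterns of mothers", together with the compliance reports.
- Section 3.4, definition of types 2a+ and 2a-: "assuming a spontaneous maturation of 1° per week", counted from 6 weeks of age. Section 1 also notes that hips mature considerably in the first weeks of life.

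The age variable named in section 3.5 and in the Annex 4 tables is age at the initial screening, not age at the follow-up scan.

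**The concern.** The duration analysis has two possible populations, and each has its own problem.

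Across both arms, swaddling days is close to a two-valued variable: none in one arm, four to six weeks in the other. Its correlation with the outcome is then largely the randomised comparison over again and says little about whether more days do more harm.

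Within the swaddled arm, exposure, exposure recording and the first scan share one 4-6 week window. A family that keeps to its instruction and is scanned at 42 days will have about 42 swaddled days; one scanned at 28 days will have about 28. The longer-swaddled infant is also the older infant, whose hip has had more time to mature. That pushes the association in the direction opposite to the trial's hypothesis. A flat or negative coefficient could then be reported as longer swaddling doing no harm. A simple Pearson coefficient has no place for the covariate that would separate the two.

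**Working it through.** **The plan's own figures.** The protocol gives no expected value for this correlation. The relevant inputs are its 10% (non-swaddled) and 40% (swaddled) risks from section 3.2. They return the stated sample size: 7.9 × (0.1×0.9 + 0.4×0.6)/0.3² = 28.97, rounded up to 29 per group. With about 40 enrolled and 20% dropout, 40 × 0.8 = 32 per arm are evaluable.

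**Which scan decides the outcome.** Non-Type 1 counts at any monthly visit, but controls continue only until Type 1 is documented. The 4-6 week scan therefore largely decides it.

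**1. Pooled over both arms.** Take 0 days in one arm and days uniform on 28-42 in the other (mean 35, variance 14²/12 = 16.3).

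- Correlation of days with arm: 17.5/√(17.5² + 16.3/2) = 0.987.
- Correlation of non-Type 1 with arm at 10% and 40%: (0.3 × 0.5)/√(0.25 × 0.75) = 0.346.
- Simulated correlation of days with non-Type 1 at those risks, with no duration effect: +0.28 to +0.33 over the models below, including early stopping and some swaddling in the non-swaddling arm. It is negative in under 1% of trials of 32 per arm. A variant that matched the arm risks only roughly gave about +0.25.
- With no arm difference it is about -0.01 to -0.03.

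So the pooled coefficient follows the arm contrast and has almost no duration content of its own.

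**2. Within the swaddled arm, no duration effect.** Two models were used, because the documents do not give the spread of alpha angles.

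*Model A.* Assumption: alpha at birth is normal, fitted to the screening figures in section 1, reading 1.2% as below 50° and 14.6% + 1.2% = 15.8% as below 60°.

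- SD = 10/(z(0.158) - z(0.012)) = 10/(-1.003 + 2.257) = 7.97; mean = 50 + 2.257 × 7.97 = 67.99.
- Restrict to 50-60° at birth and add g degrees a week. Risk at w weeks = [F(60 - g·w) - 0.012]/(0.158 - 0.012), where F is the fitted distribution function.
- At g = 1: week 4, (0.0662 - 0.012)/0.146 = 37%; week 5, (0.0516 - 0.012)/0.146 = 27%; week 6, (0.0396 - 0.012)/0.146 = 19%.
- At g = 0.5: 64%, 56%, 49%. At g = 1.25: 27%, 17%, 10%.
- With scan age uniform on 4-6 weeks and days equal to age at the scan, r = -0.12 at g = 1 (-0.08 at 0.5, -0.13 at 1.25).
- At g = 1, if 20% or 40% of swaddling families stop between days 7 and 28 (assumed), r shrinks to about -0.045 or -0.03.

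*Model B.* Assumption: average risk 40%, alpha with residual SD 2 to 4°, 32 infants.

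- At 1° a week with full adherence, mean r is -0.23 (SD 2), -0.16 (SD 3) and -0.12 (SD 4), negative in 75-91% of trials.
- With 20-40% stopping early, mean r is -0.03 to -0.10.
- At 0.5° a week with full adherence, mean r is -0.07 to -0.12.

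**3. Masking a real effect (model B, SD 3, 1° a week).** A true harm of 1° per swaddled week gives mean r = 0.00 under full adherence: harm and maturation cancel. With 20% stopping early the same harm gives about +0.19, because days then vary for reasons other than scan age.

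**4. Effect of including age at the scan.** In model A with 20% or 40% stopping early and no duration effect, the partial correlation of days with non-Type 1 given age at the scan is about 0.00. Under full adherence days and age are the same variable, and no analysis within the arm can separate them.

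**The case against.** A reader might infer that the planned correlation leans towards showing duration as protective. The documents do not support that. No section restricts the coefficient to the swaddled arm. Taken as written over both arms, at the protocol's own risks, it is clearly positive. The negative pull belongs to a within-arm analysis that the protocol leaves open but does not state.

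A reader might also infer that swaddling days is fixed by the scan date. It is not: section 3.4 takes it from diaries and compliance reports, and nothing says that swaddling stops at the scan. That days track scan age is an inference for families who comply fully. Early stopping weakens the bias to a few hundredths.

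Further objections carry weight.

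- The 1° a week is stated for the 2a+/2a- definition from 6 weeks of age; applying it from birth is an extrapolation, hence the range of rates.
- With about 32 infants, r = -0.12 is well inside sampling noise: a significant negative coefficient would appear in about 10% of trials.
- Outcome b has a second exposure, hours per day, which is not built from length of follow-up.
- Covariates for an exploratory model are often left to the SAP, which is not shown.

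The core survives these. The protocol does fix the method, a simple Pearson coefficient on days, and that method fails on either reading: pooling removes the age problem only by repeating the arm contrast.

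**Conclusion.** The point holds in this limited form: the unadjusted correlation with swaddling days does not answer secondary outcome b. Pooled, r is about +0.3 with no duration effect, because days and arm correlate at 0.987 when families adhere. Within the swaddled arm the association is biased downwards, by about -0.12 under full adherence and -0.03 to -0.05 with 20-40% stopping early in model A (up to -0.23 and -0.10 in model B). It can hide a harmful dose-response, most of all when adherence is high.

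The sizes are illustrations. They rest on an assumed alpha distribution, a maturation rate of 0.5 to 1.25° a week, scan ages spread evenly over 28-42 days and assumed stopping patterns. The within-arm direction is the same throughout when there is no duration effect; the size is not firm.

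The primary intention-to-treat comparison and the sample size are untouched. This is a cheap improvement.

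**What to change.** Change the wording in sections 3.4 and 3.5.

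- Replace the Pearson coefficient for duration with a logistic exposure-response model of non-Type 1, within the swaddled arm or in both arms with arm as a term, and state which.
- Include age in days at the follow-up scan as a covariate.
- Express exposure up to the scan as mean swaddled hours per day or as the share of days swaddled.
- State that the estimate is informative only to the extent that adherence varies. The share of days equals 1 for every full complier, so changing the exposure measure alone does not create dose information; the age term is the essential part.

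The cost is small. Birth date is already collected (section 3.3), and age at the scan follows from the scan date. The downside is that an absolute number of days is no longer the main exposure measure; it can still be reported descriptively.
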